## **8.8 Prior and Concomitant Medications**

Prior and concomitant medications recorded during the study will be coded with the World Health Organization (WHO) Drug Dictionary Version 01-Sep-2023\_b3 and listed.

## **8.9 Physical Examination**

Abnormal physical examination findings will be reported as medical history or AEs. All data found in the CRF will be listed.

## **9. SUMMARY OF CHANGES FROM PROTOCOL-PLANNED ANALYSIS**

The protocol states that the following safety data will be summarized: physical examinations, medical history, disease history, concomitant medications, SAEs, AEs leading to discontinuation from study, AEs leading to discontinuation of study product, AEs within a specified time interval from dosing, and lab abnormalities (by severity). However, these analyses will not be performed and are not included in this SAP.

The protocol states that the all subjects receiving TRL345 will be included in the analyses. However, the Pharmacokinetic Population and the Pharmacokinetic Analysis Population were defined in this SAP for the PK analyses.

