8.5 Safety Analyses

8.5.1 Adverse Events

All AEs, including IRs, and SAEs, will be coded using the Medical Dictionary for Regulatory Affairs (MedDRA). Frequency tables will be presented by dose and treatment group for all AEs and SAEs by System Organ Class (SOC) and Preferred Term (PT). Frequency tables will also be produced by dose and treatment group for AEs leading to discontinuation from IP and study, by maximum severity, and by causality. No formal statistical testing will be done.

AEs and SAEs will be summarized overall, by severity, and relatedness, and may also be summarized within specific time intervals (e.g., within 4 hours of infusion).

Clinically significant physical exam and lab abnormalities will be reported as AEs and summarized as described above.

8.5.2 *Laboratory Evaluations and Vital Signs*

Quantitative data (e.g., clinical lab results) will be summarized by presenting mean, median, SD, and range by dose and treatment group. Laboratory abnormalities will be analyzed as safety outcomes by summarizing frequency, severity, and changes from baseline. Other analyses may include but are not limited to the following: examination of shift tables and pre-established severity grades. Additional serum samples will be taken and stored for possible exploratory analyses that may be necessary to further explore any unexpected safety or tolerability observations.

8.5.3 *Concomitant Medications*

Concomitant medications will be coded using the most current World Health Organization (WHO) drug dictionary and summarized by drug class and medication term, with results presented by dose and treatment group.

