## 2. OBJECTIVES AND ENDPOINTS

Objectives	Endpoints
Primary	
To assess the safety and tolerability of TRL345 when administered intravenously (IV) as a single dose in healthy adult volunteers	Incidence and severity of abnormal physical exam findings, serum chemistries and hematology, vital signs (temperature, blood pressure, heart rate), adverse events (AEs), and incidence of serious adverse events (SAEs)
Secondary	
To characterize the pharmacokinetics (PK) of a single IV infusion of TRL345 overall and by dose group (DG)	$C_{max}$ , $C_{min}$ , CL, $V_{ss}$ , and $t_{1/2}$ , overall and by DG will be calculated by using serum concentrations of TRL345 determined by an enzyme-linked immunosorbent assay (ELISA)
To assess the immunogenicity of TRL345 as measured by anti-drug antibodies (ADAs)	Incidence of baseline and investigational product (IP)-emergent ADA (i.e., anti-TRL345 antibodies) in serum will be determined by an ELISA method.

Objectives	Endpoints
Exploratory	
To explore the pharmacodynamics (PD) of TRL345 in an ex vivo study using serum samples to explore the capacity of various concentrations of TRL345 to neutralize human cytomegalovirus (HCMV) in human serum*	The proportion of samples with TRL345 concentrations within prespecified ranges that are associated with neutralization of HCMV in human serum
To explore if there are any differences in AEs, clinical labs, or PK across DGs to explore if there are any signs of off-target binding of TRL345	Gastrointestinal and central nervous system (CNS) AEs will be compared across DGs for any qualitative or quantitative differences in such events. Lactic acid dehydrogenase (LDH), high-sensitivity C-reactive protein (hsCRP), interleukin (IL)-1alpha, estimated AUC, and estimated t 1/2 will also be compared across DGs.

Note: \* This objective is not covered by this SAP as this analysis will not be performed by Celerion. The results for this objective will not be reported in the Celerion provided CSR.

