## **8.4 Adverse Events**

All AEs occurring during this clinical trial will be coded using the Medical Dictionary for Regulatory Activities (MedDRA®), Version 26.1.

All AEs captured in the database will be listed in a by-subject data listing including dose group, verbatim term, coded term, treatment, onset date/time, resolution date/time, frequency, severity, relationship to study product, action, and whether the AE is an IR; however, only treatment-emergent AEs (TEAEs) will be summarized.

A TEAE is defined as an AE that is starting at the time of or after the start of study product administration. Each TEAE will be attributed to the treatment based on the onset date and time of the AE compared to that of the respective treatment administration start date and time.

If the onset time of an AE is missing and the onset date is the same as or occurs after the treatment dosing date, then the AE will be considered treatment emergent. If the onset date of an AE is missing, then the AE will be considered treatment emergent.

TEAEs will be tabulated by System Organ Class (SOC) and Preferred Term. Summary tables will include the number of subjects reporting the TEAE and as a percent of the number of subjects dosed by treatment (pooled placebo, active treatment, active treatment total) and

overall. The number of TEAEs will be tabulated in a similar manner. A table, which summarizes the number of TEAEs by Preferred Term, severity, and relationship to study product, will also be included.

SAEs if present, will also be listed. Applicable narratives will be included in the CSR.

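### Incidence of SAEs is part of the primary endpoint, but SAP 9 cancels its summary by treatment; abnormal physical-exam findings have no summary of their own

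*SAP*

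**What the plan says.** **Endpoint.** The primary endpoint in SAP 2, which follows protocol 2.2.1, opens with "Incidence and severity of abnormal physical exam findings, serum chemistries and hematology" and ends with "and incidence of serious adverse events (SAEs").

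**Protocol analysis.** Protocol 8.5.1 states: "Frequency tables will be presented by dose and treatment group for all AEs and SAEs by System Organ Class" and Preferred Term. The protocol synopsis also promises frequencies and percentages of subjects with SAEs by dose group, and descriptive statistics for physical-exam findings by dose group.

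**SAP analysis.** SAP 9 lists summaries that the protocol planned, among them "physical examinations, medical history, disease history, concomitant medications, SAEs, AEs leading to discontinuation from study", and then says: "However, these analyses will not be performed and are not included in this SAP". SAP 8.4 gives the remaining output for serious events: "SAEs if present, will also be listed". SAP 8.9 covers exams: "Abnormal physical examination findings will be reported as medical history or AEs", with the CRF data listed.

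**The concern.** SAP 2 still promises an incidence that SAP 9 removes. SAP 9 discloses the change but gives no reason for it, and SAP 2 was not edited to match. In a first-in-human trial whose primary objective is safety, SAE incidence is among the first results a reader looks for. Under the current plan it would be reported with no denominator by treatment. If no SAE occurs, the SAE detail listing (Appendix 16.2.7.2) is dropped and Table 14.3.2.1 shrinks to one sentence.

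The exam component has a related but smaller problem. The endpoint speaks of abnormal findings, while the route into a table is open only to findings that become adverse events.

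**Working it through.** **Step 1. Denominators.** SAP 3 gives 6 TRL345 and 2 placebo subjects in each of two dose groups. Total = 2 × (6 + 2) = 16, which matches the planned 16. With placebo pooled (SAP 5): P = 2 × 2 = 4, A = 6, B = 6, Active Total = 12, Overall = 16.

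**Step 2. Where an SAE would appear.**

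| Output | Content | SAE n (%) by treatment? |
|---|---|---|
| Table 14.3.2.1 | Listing in the Appendix 16.2.7 format, or a no-events sentence | No |
| Appendix 16.2.7.2 | By-subject SAE details, removed if there are none | No |
| Tables 12-1 and 14.3.1.1 | Subjects with TEAEs, n (%) | No; serious events not separated |
| Table 14.3.1.2 | Number of TEAEs | No; serious events not separated |
| Table 14.3.1.3 | TEAEs by severity grade and relationship | No; severity grade is not seriousness |

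Planned tables with an SAE rate by treatment: 0.

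**Step 3. Where an abnormal exam finding would appear.**

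- *New and clinically significant, after Day 1.* Protocol 7.4 makes it an adverse event, and protocol 8.5.1 says such findings are summarized with the adverse events. It is counted by treatment in four tables (12-1, 14.3.1.1, 14.3.1.2, 14.3.1.3). Two of these (12-1 and 14.3.1.1) give the percent of subjects dosed. In none can it be recognized as an exam finding.
- *Abnormal but not clinically significant.* It is listed in Appendices 16.2.4.2 to 16.2.4.4. The shell for 16.2.4.4 uses such a finding as its example. No table counts it.
- *Section 14.3.5.* The heading includes physical examination, but the tables under it cover only laboratory tests, vital signs and ECG.

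Planned tables with an incidence of abnormal exam findings as such: 0.

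**Step 4. Routing.** Protocol 7.4 sends clinically significant findings to medical history (Day 1) or to adverse events (new, after Day 1). SAP 8.9 sends abnormal findings to one or the other without that qualifier. The two rules differ for a non-significant finding.

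**Step 5. What the missing SAE row would show.** One subject with an SAE would be 1/4 = 25% (P), 1/6 = 17% (A or B), 1/12 = 8% (Active Total) or 1/16 = 6% (Overall).

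For context only, zero SAEs in n subjects has an exact two-sided 95% upper limit of 1 − 0.025^(1/n):

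| n | Upper limit for 0/n |
|---|---|
| 4 | 60% |
| 6 | 46% |
| 12 | 26% |
| 16 | 21% |

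These limits reflect the size of the study, not the cancelled summary.

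**The case against.** The case for leaving the plan alone has four parts.

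1. **Little is lost in practice.** There are 16 subjects. The SAE listing shows dose group, subject and treatment, and the disposition and TEAE tables give the denominators. A no-events sentence together with those denominators is 0/N in each group. Any treatment-emergent SAE is also counted among the TEAEs. All this is true and limits the weight of the point. It does not remove the conflict: the plan names an incidence and cancels the only output that would state it.

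2. **Exam findings are covered through adverse events.** A reader might infer that this component has no rate by treatment at all. The documents do not support that. The synopsis criteria for evaluation fold exam findings into adverse events, and protocol 7.4 and 8.5.1 and SAP 8.9 carry this out for clinically significant ones. What stands is narrower: there is no separate exam-finding incidence and no count of non-significant findings, although the synopsis also promises a descriptive summary of exam findings by dose group.

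3. **Confidence intervals were never planned.** A reader might infer that the cancellation removes interval estimates. It does not. Protocol 8.2 limits categorical summaries to counts and percentages, and protocol 8.5.1 rules out formal testing. Restoring the protocol's table would give n (%) only. This objection stands in full.

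4. **An exam row would not fit the TEAE table.** Non-significant findings are not adverse events, and significant ones would be counted twice. Post-dose exams are targeted and only Screening has a complete exam, so a new-abnormality count depends on which systems were examined. This stands too, and it shapes the fix.

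**Conclusion.** The point holds for SAEs. Incidence of SAEs is a named part of the primary endpoint, protocol 8.5.1 asks for frequency tables, and SAP 9 cancels them, leaving no n (%) by treatment. For physical exams it holds in limited form: significant findings are counted as undifferentiated TEAEs, non-significant ones are only listed, and SAP 2, SAP 8.9, SAP 9 and protocol 7.4 do not agree on what the component covers.

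This is a reporting gap worth closing before the SAP is used. It is not a loss of data, and sample size and design are unaffected. The conclusion rests on the table list in SAP 10 and the shells in SAP 11 being complete for these outputs. SAP 11 allows shells to change, but SAP 9 states the omission outright. The denominators assume enrollment as planned, with no replacement subjects and no expanded dose group.

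**What to change.** **SAEs.** Delete SAEs from the SAP 9 list of analyses not performed. Add one row to Table 14.3.1.1 for subjects with at least one treatment-emergent SAE, n (%), for P, A, B, Active Total and Overall (planned denominators 4, 6, 6, 12, 16). Print the row even when every count is zero. Protocol 7.1 records adverse events from the start of infusion, so limiting the row to treatment-emergent events should lose nothing.

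**Physical exams.** Choose one of two options:

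- add a short separate table under 14.3.5 with n (%) of subjects with a new post-dose abnormal finding by treatment, with a stated rule for what counts as new given that post-dose exams are targeted; or
- state in SAP 2 that this component is assessed through TEAEs, and keep the SAP 9 entry.

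In either case, align SAP 8.9 with protocol 7.4 on whether only clinically significant findings become medical history or adverse events.

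Exact confidence intervals may be added but are optional.

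**Cost.** One row in an existing table, a few sentences of text and at most one small table. The data are already collected.

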2 OBJECTIVES AND ENDPOINTS

2.1 Objectives

2.1.1 *Primary Objective*

- Assess the safety and tolerability of TRL345 when administered intravenously (IV) as a single dose in healthy adult volunteers

2.1.2 *Secondary Objectives*

The secondary objectives are to:

- Characterize the pharmacokinetics (PK) of a single IV infusion of TRL345 overall and by DG
- Assess the immunogenicity of TRL345 as measured by anti-drug antibodies (ADAs)

2.1.3 *Exploratory Objective*

The exploratory objectives are to:

- Explore the pharmacodynamics (PD) of TRL345 in an *ex vivo* study using serum samples to explore the capacity of various concentrations of TRL345 to neutralize HCMV in human serum
- Explore if there are any differences in adverse events, clinical labs, or PK across dose groups to explore if there are any signs of off-target binding of TRL345

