7.1 Reporting Responsibilities

All AEs, including SAEs, will be recorded in the eCRF from start of IP infusion through Study Day 76. It is the responsibility of the Investigator or Sub Investigator(s) to perform assessment of AEs and SAEs at each study visit. Data describing AEs, and SAEs, will be entered in the subject’s medical record and eCRF. SAEs will be reported to the Sponsor as described in [Section 7.6](#).

Subjects who experience AEs, whether serious or not serious, should receive appropriate treatment and medical supervision as clinically indicated. All AEs must be followed until resolution/stabilization or until a time that is mutually agreed upon between the Medical Monitor and the Investigator.

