### **6.3 Pharmacokinetic Concentrations**

#### **Measurements and Collection Schedule**

Blood samples for the determination of TRL345 in serum will be collected for all subjects at the following time points:

- Day 1: Predose (imputed as time 0) and approximately 1 hour  $\pm$  15 minutes (end of infusion [EOI]), 2 hours  $\pm$  15 minutes, 4 hours  $\pm$  15 minutes, 6 hours  $\pm$  15 minutes, and 12 hours  $\pm$  15 minutes post-start of infusion (SOI)
- Days 2 (24 hours  $\pm$  1 hour post-SOI), 3 (48 hours  $\pm$  1 hour post-SOI), 8 (168 hours post-SOI), 15 (336 hours post-SOI), 29 (672 hours post-SOI), 43 (1008 hours post-SOI), and 76 (1800 hours post-SOI)

All concentration data, as received from the bioanalytical lab, will be listed by subjects, treatment, and nominal time in an appendix. If there are any significant protocol deviations (e.g., significant time deviations from nominal sample times), some individual concentration data may be excluded from mean data presentations (e.g., descriptive statistics for concentrations at specific nominal time points and mean concentration-time plots). No concentration values will be imputed for missing or not reported samples (NS or NR), unless predose. All deviations and excluded data will be provided and discussed in the CSR.

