Appendix 16.2.7.1 Adverse Events (Safety Population)

Dose Group	Subject Number	Age/ Sex	Treatment	TE?	System Organ Class/ Preferred Term (Verbatim)	Time From Last Dose (DD:HH:MM)	Date:Time Start/ End Duration (DD:HH:MM)	Serious/ Outcome	Severity/ Frequency	Study Product Relationship/ Action	IR?*
1	0001	30/F			None						
	0002	24/M			None						
	0003	52/M	A	Yes	XXXXXXXXXXXXX/ XXXXXXXXXXXXXXXXX (XXXXXXXXXXXXX)	XX:XX:XX	DDMONYYYY:HH:MM/ DDMONYYYY:HH:MM 00:23:15	No/ Recovered/ Resolved	Moderate (Grade 2)/ Intermittent	Likely/ Drug Withdrawn	No
				Yes	<similar to above>						

Programmer Note: AEs should be presented start date/time order for each subject.

Treatment A: < >

Treatment B: < >

Treatment P: < >

Adverse events are classified according to MedDRA Version 26.1.

\*Is adverse event an infusion reaction?

TE = Treatment-emergent

F = Female; M = Male

Source: SDTM.< >; ADaM.< >

Program: /CAXXXXX/sas\_prg/stsas/lis/programname2022Q1.sas DDMONYYYY HH:MM

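### No planned table gives the incidence of infusion reactions or acute-onset AEs, because SAP 9 drops the optional summary by time from dosing and the infusion-reaction flag is only listed

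*SAP*

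**What the plan says.** The primary objective (Protocol 2.1.1) is: "Assess the safety and tolerability of TRL345 when administered intravenously (IV) as a single dose in healthy adult volunteers". Protocol 7.1 sets the collection period: "All AEs, including SAEs, will be recorded in the eCRF from start of IP infusion through Study Day 76".

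On timing, Protocol 8.5.1 says that AEs and SAEs "may also be summarized within specific time intervals (e.g., within 4 hours of infusion"). SAP 9 describes this as something the protocol says will be summarized, then removes it in a list of dropped items that ends: "AEs within a specified time interval from dosing, and lab abnormalities (by severity). However, these analyses will not be performed". It gives no reason.

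SAP 8.4 sets no upper time limit on treatment emergence: "A TEAE is defined as an AE that is starting at the time of or after the start of study product administration". The same section places the infusion-reaction flag in the listing: "whether the AE is an IR; however, only treatment-emergent AEs (TEAEs) will be summarized".

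The planned AE tables are in-text Table 12-1 and Tables 14.3.1.1 to 14.3.1.3. Their shells have rows by organ class and preferred term. Table 14.3.1.3 adds columns for severity grade and for likely or unlikely relationship. None has an onset window or an infusion-reaction row. Onset relative to dosing appears once, as the column "Time From Last Dose" in the listing shell for Appendix 16.2.7.1.

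**The concern.** This is a first-in-human IV infusion, and the protocol treats the infusion as a specific risk. It asks for close monitoring from the onset of infusion, notice of any infusion-related AE to the Safety Monitoring Committee within 24 hours, and a separate eCRF page for infusion reactions (Protocol 3.1, 3.4, 5.7). A reader of the report will want to know how many subjects on each dose, and on placebo, had a reaction or an acute AE. The data to answer this are collected, but no planned table does so.

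Without an onset window, nausea or headache during the infusion is counted in the same row as nausea or headache weeks later. With 6 subjects per dose and 4 on pooled placebo, a few late background events can hide or mimic an acute difference. SAP 1 puts exploratory analyses not covered by the SAP out of scope, so a window added later would be chosen after the data were seen.

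**Working it through.** **Length of the counting period.** Day 1 to Day 76 is (76 − 1) × 24 = 1800 hours, or 75 days. This matches the SAP's own figure in its sampling schedule ("and 76 (1800 hours post-SOI"). A 4-hour window is 4/1800 = 0.22% of that period.

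**Subjects.** Two dose groups of 6 active and 2 placebo give 12 active and 4 pooled placebo (SAP 3 and 5).

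**Assumptions.** The documents give no AE rates. I assume that TRL345 causes an acute AE in 25% of subjects, independently of background. I also assume that a proportion b of subjects have at least one background AE by Day 76, at constant hazard.

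**Formulas.**
- Background hazard per day: h = −ln(1 − b)/75
- Placebo risk in a window of w days: p0 = 1 − exp(−h·w)
- Active risk: p1 = 1 − (1 − p0)(1 − 0.25)
- SE = √[p1(1 − p1)/12 + p0(1 − p0)/4]
- Reversal chance: probability that the placebo percentage equals or exceeds the active percentage, from exact binomials with n = 4 and n = 12

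**Worked case, b = 50%, any-AE row.**
- To Day 76: p0 = 0.50 and p1 = 1 − 0.50 × 0.75 = 0.625. The difference is 12.5 points. SE = √(0.625 × 0.375/12 + 0.50 × 0.50/4) = 28.6 points. Ratio 0.44.
- 0-24 h: h = 0.00924, p0 = 0.0092 and p1 = 1 − 0.9908 × 0.75 = 0.257. The difference is 24.8 points and SE 13.5 points. Ratio 1.84.

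**Range for the any-AE row.**

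| Background by Day 76 | Ratio, Day 76 | Reversal chance, Day 76 | Ratio, 0-24 h | Reversal chance, 0-24 h |
|---|---|---|---|---|
| 30% | 0.65 | 30% | 1.91 | 4% |
| 50% | 0.44 | 39% | 1.84 | 5% |
| 70% | 0.29 | 47% | 1.74 | 6% |

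With no background at all the ratio would be 0.25/√(0.25 × 0.75/12) = 2.0, which is the ceiling under these assumptions.

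**Single-term rows.** Suppose the whole 25% effect falls in one preferred term. The same formulas with p0 set to that term's 75-day background give:
- 2% background: ratio 1.69, reversal chance 7%
- 5%: 1.40, 12%
- 10%: 1.11, 18%

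An effect spread over several terms would show less in each row.

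**Front-loaded background.** If the 24-hour placebo risk itself is 10% or 20%, the 24-hour ratio becomes 1.11 or 0.82 and the reversal chance 18% or 25%.

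The ratio is used here only to measure how clearly a difference would stand out in a descriptive table. Protocol 8.5.1 plans no formal testing of AEs.

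**The case against.** The case for leaving the plan alone has several good parts.

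- The protocol wording is permissive, and SAP 9 declares the omission. A reader might infer a departure from a required analysis, partly because SAP 9 itself overstates the protocol. No required analysis or endpoint is lost. This stands.
- A reader might infer that all AEs fall into one undifferentiated count. They do not. A rash at 30 minutes and a cold on Day 60 sit in different organ-class and preferred-term rows and meet only in the any-AE row. Table 14.3.1.3 also separates likely from unlikely events, and timing is the first reason that Protocol 7.2.3 gives for a likely relationship. This stands, but relatedness is a judgement and not an onset window, and a term that occurs early and late is still merged.
- A reader might infer that the planned tables cannot show an acute contrast. The single-term figures show that they can when the effect is concentrated in a term with little background.
- Constant hazard favours the 24-hour window. Day 1 has the infusion, repeated blood draws and close observation, whereas later AEs are assessed at visits. Background may therefore be front-loaded, which is why the 10% to 20% case is shown. Even at 20%, the 24-hour ratio of 0.82 exceeds the highest any-AE figure of 0.65, though the gain is then modest.
- A reader might infer that acute data are lost. They are not. The listing carries treatment, time from dose and the infusion-reaction flag for each AE, and 16 subjects can be counted by hand. Vital signs are tabulated through 5 hours after the start of infusion (SAP 8.6), although as descriptive statistics and not as AE incidence.

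**Conclusion.** The point holds as a gap in reporting. SAP 9 drops an optional summary, and no other planned table gives the incidence of infusion reactions or acute-onset AEs, although infusion tolerability belongs to the primary objective. The mixing of acute and background events is greatest in the any-AE row (ratio 0.65 to 0.29, against 1.91 to 1.74 in a 0-24 h window) and smaller in single-term rows (1.69 to 1.11 at 2% to 10% background). All these figures rest on the assumed 25% acute effect and the assumed backgrounds; the 24-hour range also rests on constant hazard, and falls to 1.11 to 0.82 if first-day background is 10% to 20%. The documents do not support calling this a protocol breach, a loss of data or an inability to see acute effects. The gain is a prespecified descriptive count that readers would otherwise have to build from the listing.

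**What to change.** Remove the item on AEs by time interval from the list of dropped analyses in SAP 9. Add one descriptive table with columns P, A, B and Active Total, showing the number and percentage of subjects with:

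- at least one TEAE with onset 0-4 h, 0-24 h, and more than 24 h to Day 76, all measured from the start of infusion;
- at least one TEAE flagged as an infusion reaction.

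Give preferred-term rows only for terms observed in the 0-24 h window, to keep the table short. Because SAP 8.4 counts AEs with a missing onset date, or a missing time on or after the dosing date, as treatment-emergent, add a line saying where such events go.

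The cost is SAP wording and one table from variables already planned for Appendix 16.2.7.1, with no new data and no protocol change. The table will be sparse and imprecise: 0 of 6 has an exact 95% upper limit of 46%, and 0 of 4 one of 60%. It should be presented as description only.

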## **8. SAFETY**

All relevant case report form (CRF) and clinical laboratory data will be listed by subject and chronologically by assessment time point. This will include rechecks, unscheduled, and early termination assessments.

Applicable continuous variables will be summarized using n, mean, SD, minimum, median, maximum, and range. Data from subjects who received the placebo treatment will be pooled across dose groups.

The level of precision will be presented as follows: minimum/maximum/range in the same precision as in the database, mean/median in one more precision level than minimum/maximum/range, SD in one more precision level than mean/median, and n will be presented as an integer. Percentages will be presented as an integer.

Where individual data points are missing because of dropouts or other reasons, the data will be summarized based on reduced denominators.

Baseline will be the result closest and prior to start of dosing unless otherwise stated. Summaries for post-baseline time points will not include rechecks, unscheduled, or early termination measurements.

Tables summarizing safety data by assessment time point will only include summaries for baseline and post-baseline time points.

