## 8.5 Clinical Laboratory Tests (Chemistry and Hematology)

Clinical laboratory tests will be measured at the following time points:

Clinical Laboratory Panels	Time Point		
	Period	CRF/Listing Day and Hour	Table
Chemistry, Hematology	Screening		NA
	1	Day -1 Hour -23.00/-22.75*^	Baseline
		Day 2 Hour 24.00	Day 2
		Day 3 Hour 48.00^	Day 3
		Day 8 Hour 168.00	Day 8
		Day 15 Hour 336.00*^	Day 15
		Day 29 Hour 672.00*^	Day 29
		Day 43 Hour 1008.00^	Day 43

Time points in the CRF/Listing column are approximated/based on the blank CRF and it should be noted that the data listings will reflect the data found in the final subject CRFs.

If applicable, an early termination assessment will be performed.

\*hsCRP and LDH will be collected at these time points and included in the Chemistry TFLs.

^NT-proBNP and IL-1 $\alpha$  will be collected at these time points and included in the Chemistry TFLs.

NA = Not applicable (individual result(s) may be required for baseline)

Clinical laboratory results will be presented in standard international (SI) units. Out-of-reference range flags will be recorded as follows: high (H) and low (L) for numerical results and did-not-match (\*) for categorical results.

Out-of-reference range values and corresponding recheck results will be listed.

For all numeric laboratory values, descriptive statistics will be presented for each laboratory test by assessment time point and treatment (pooled placebo and active treatment). Change from baseline will be summarized in a similar manner. For all numeric laboratory tests, the mean value calculated for each assessment time point and treatment will be compared to the reference range and flagged if outside of the reference range (\* if above the reference range and ^ if below the reference range). In the event there is more than one reference range for a laboratory test, the comparison will be made against the lowest of the lower ranges and the highest of the higher ranges.

For each laboratory test, a shift table will be developed to compare the frequency of the results at baseline (above reference range, within reference range, or below reference range) with the respective postdose results.

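### The primary endpoint keeps severity of abnormal labs and vital signs, but no planned table gives subjects by laboratory grade, subjects with abnormal vital signs, or subjects by maximum AE severity

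*SAP*

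**What the plan says.** **Endpoint.** SAP 2 repeats Protocol 2.2.1 and opens the primary endpoint with "Incidence and severity of abnormal physical exam findings, serum chemistries and hematology, vital signs". AEs and SAEs follow as further items.

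**Laboratory results.** Protocol 8.5.2 states: "Laboratory abnormalities will be analyzed as safety outcomes by summarizing frequency, severity, and changes from baseline". SAP 9 withdraws the severity part. Its list of cancelled summaries, which also includes SAEs and physical examinations, ends "and lab abnormalities (by severity). However, these analyses will not be performed and are not included in this SAP". In SAP 8.5, "a shift table will be developed to compare the frequency of the results at baseline" with post-dose results. The categories are low, within range and high, without grades. Descriptive statistics and by-subject tables of out-of-range values are also planned.

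**Vital signs.** SAP 8.6 and Table 14.3.5.5 (shell CVS) plan descriptive statistics and change from baseline. No limit for an abnormal post-dose value is defined.

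**Values used.** SAP 8 states: "Summaries for post-baseline time points will not include rechecks, unscheduled, or early termination measurements".

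**Adverse events.** Protocol 8.5.1 promises frequency tables "by dose and treatment group for AEs leading to discontinuation from IP and study, by maximum severity, and by causality". SAP 8.4 offers instead: "A table, which summarizes the number of TEAEs by Preferred Term, severity, and relationship to study product, will also be included". Its shell, CAESR, gives the number of subjects and of events per Preferred Term, and is titled as a count of events when it splits by grade and relationship. SAP 9 does not mention the maximum-severity table.

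**The concern.** Safety is the only primary objective and no formal testing is planned, so the descriptive tables are the primary analysis. With six active subjects per dose, a safety signal is likely to be one or two people with a graded abnormality. The useful number is then how many subjects reached each grade. The SAP leaves the endpoint wording intact but removes the laboratory severity summary, and it never sets up a count of abnormal vital signs. The study report would name an endpoint that its tables only partly report. A reader would have to rebuild the missing counts from listings, using limits chosen after the data are seen.

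**Working it through.** The documents give no sample-size or precision figure to reproduce. The check matches each endpoint component to the planned output and then asks what the remaining tables can and cannot show.

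**1. Endpoint components against planned summaries (SAP 8 to 11)**

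| Component | Direct summary table |
|---|---|
| AE incidence | Yes: 14.3.1.1, 14.3.1.2 |
| AE severity | Yes, as events by grade: 14.3.1.3 |
| SAE incidence | No: listed in 14.3.2.1 |
| Laboratory abnormality, incidence | Yes, by visit: 14.3.5.2, 14.3.5.4 |
| Laboratory abnormality, severity | No: cancelled in SAP 9 |
| Vital-sign abnormality, incidence | No |
| Vital-sign abnormality, severity | No |
| Physical exam abnormality, incidence | No: listed, or recorded as AE or medical history |
| Physical exam abnormality, severity | No: as above |

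Three of nine have a direct summary.

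**2. Weight of one subject.** Each dose group has 6 active and 2 placebo subjects. One subject is 1/6 = 16.7% of an active group, 1/12 = 8.3% of Active Total and 1/4 = 25% of pooled placebo.

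**3. Laboratory tables**

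- *Flag on the mean (shell CLBD).* Suppose five subjects sit at a multiple a of the upper limit of normal (ULN) and the sixth at x. The mean reaches the limit when (5a + x)/6 = 1, so x = 6 − 5a. The value of a is an assumption: a = 0.5 gives x = 3.5, a = 0.8 gives 2.0 and a = 0.9 gives 1.5. The flag is therefore a weak detector. The same shell prints the minimum, maximum and range, so the extreme scheduled value is visible.
- *Shift table (shell CLBS).* Results of 1.05 × ULN and 8 × ULN fall in the same high cell. Read with the maximum, the table gives the number of subjects above range and the largest value at that visit. It does not give the number at each grade.
- *Across visits.* There are six post-dose visits (Days 2, 3, 8, 15, 29, 43). If each shows one high result in a group of six, between 1 and 6 different subjects were ever high, or 17% to 100%. Tables 14.3.4.1 and 14.3.4.2 would settle this, but only by hand count.

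**4. Vital signs.** CVS gives the minimum and maximum at 11 post-baseline time points (five on Day 1, then Days 2, 3, 8, 15, 29, 43). No shift table or by-subject out-of-range table exists. Listing 16.2.8.6 marks rechecks but carries no high or low flag. A vital sign measured only at an unscheduled or early-termination assessment appears in that listing and in no summary.

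**5. Adverse events by grade.** Take a CAESR row with 2 subjects and 4 events, two of Grade 1 and two of Grade 2. Two situations give this same row:

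- One subject had both Grade 2 events. By maximum severity, one subject is at Grade 1 and one at Grade 2 (1/6 = 17% at Grade 2).
- Each subject had one event of each grade. By maximum severity, both are at Grade 2 (2/6 = 33%).

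The protocol's own pausing criteria (3.6) depend on how many subjects have a Grade 2 event, so the distinction matters on the protocol's terms.

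**The case against.** The strongest defence is that the information is already there.

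- Laboratory incidence by visit is in the shift tables.
- CLBD and CVS print the maximum, so a large scheduled value cannot disappear.
- Out-of-range laboratory values, including unscheduled and early-termination ones, appear by subject with treatment in Tables 14.3.4.1 and 14.3.4.2.
- Clinically significant laboratory and physical exam findings become AEs (Protocol 7.3, 7.4, 8.5.1) and so reach the TEAE tables, where CAESR splits events by grade. The protocol synopsis even places labs and vital signs inside the AE criterion.
- The laboratory change is openly declared.
- The protocol's analysis text promised only descriptive statistics for vital signs, so SAP 9 cancels nothing there.
- Escalation rests on unblinded committee review of all available safety data, not on these tables.

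All of these statements are correct, and they limit the point. They do not remove it. The AE route needs a laboratory finding to be confirmed by repeat and judged to warrant a change in management (Protocol 7.3), so it is a subset of abnormal results. Neither 7.3 nor 7.4 covers vital signs, and only the synopsis puts them within AEs, whereas Protocol 2.2.1 and SAP 2 list them separately. A maximum is one value and not a count of subjects. Declaring a change explains the missing laboratory table but leaves the endpoint wording unmet. The maximum-severity omission is not declared at all.

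**Conclusion.** The mismatch is real and should be corrected before database lock. Laboratory severity, and both incidence and severity of abnormal vital signs, remain in the primary endpoint without a subject-level summary. The AE table by maximum severity has dropped out undeclared. SAE incidence is reduced to a listing. Post-baseline summaries use scheduled values only.

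Four stronger conclusions are tempting, and the documents do not support them:

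- *That laboratory safety is never analysed.* Shift tables, descriptive statistics and the AE route remain.
- *That the tables cannot show an extreme value.* A scheduled one appears as the maximum. The 3.5 × ULN figure concerns only the flag on the mean and depends on the assumed 0.5 × ULN for the other five subjects.
- *That one subject with five mild events cannot be told from five subjects with one each.* CAESR gives subjects and events per Preferred Term, so these read 1 and 5 against 5 and 5. What is missing is subjects by grade.
- *That unscheduled laboratory results are confined to appendix listings.* Out-of-range ones are in the Section 14 by-subject tables.

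The conclusion rests on the table shells as printed. The SAP says these show general layout and may change. It does not depend on any assumed event rate.

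**What to change.** 1. In SAP 9, delete laboratory abnormalities by severity and SAEs from the cancelled analyses. The time-interval AE summaries can stay out, since Protocol 8.5.1 makes them optional.
2. Add n (%) of subjects by worst post-dose grade for each laboratory test and vital sign covered by the scale named in Protocol 7.2.4. That section applies the scale to reported signs and symptoms, so the sponsor should first confirm which tests it covers. For tests it does not cover, give n (%) outside the reference range with the worst multiple of the limit. For any vital sign it does not cover, write the limits into SAP 8.6 in advance.
3. Base these tables on all post-dose values, including unscheduled, recheck and early-termination values, for P, A, B and Active Total. Keep the by-visit tables as planned.
4. Add TEAE tables counting subjects by maximum severity and by relationship, and counts of subjects with SAEs and with infusion reactions. The infusion-reaction indicator is already in the AE listing.

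The cost is SAP wording and a few tables from data already collected. One side effect needs a footnote: worst-value summaries that include unscheduled results will show somewhat more abnormalities in subjects who are retested more often.
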